12.15. Appendix 15: Likert Patient Depressive Symptom Scales (Part B Only)

ALLERGAN 3125-104-002 PART B
Likert Patient Depressive Symptom Scales (Clinic Evaluation)
Screening

INSTRUCTIONS:

- Please complete all questions
- Read each question carefully
- Pay close attention to the specific time frame in each question
- For each question, circle the number from zero to ten, that best describes your symptoms and how you have been feeling, on average, during the time frame.

Difficulty falling asleep
 Please rate your difficulty of falling asleep in the last 7 days

[figure not shown]

A horizontal Likert scale with 11 points labeled 0 through 10. The scale is divided into five categories: 'No difficulty' (0-2), 'mild difficulty' (3-4), 'moderate difficulty' (5-6), 'severe difficulty' (7-8), and 'Very severe difficulty' (9-10).

0 1 2 3 4 5 6 7 8 9 10

No difficulty mild difficulty moderate difficulty severe difficulty Very severe difficulty

Difficulty staying asleep
 Please rate your difficulty of staying asleep in the last 7 days

[figure not shown]

A horizontal Likert scale with 11 points labeled 0 through 10. The scale is divided into five categories: 'No difficulty' (0-2), 'mild difficulty' (3-4), 'moderate difficulty' (5-6), 'severe difficulty' (7-8), and 'Very severe difficulty' (9-10).

0 1 2 3 4 5 6 7 8 9 10

No difficulty mild difficulty moderate difficulty severe difficulty Very severe difficulty

Problems waking up too early
 Please rate your problems waking up too early in the last 7 days

[figure not shown]

A horizontal Likert scale with 11 points labeled 0 through 10. The scale is divided into five categories: 'No problems' (0-2), 'mild problems' (3-4), 'moderate problems' (5-6), 'severe problems' (7-8), and 'Very severe problems' (9-10).

[figure not shown]
0 1 2 3 4 5 6 7 8 9 10

No problems mild problems moderate problems severe problems Very severe problems

[figure not shown]
Overall Depression
Please rate your overall feelings of depression in the last 7 days

[figure not shown]
Overall Anxiety
Please rate your overall feelings of anxiety in the last 7 days

[figure not shown]
Overall Irritability
Please rate your overall feelings of irritability in the last 7 days

[figure not shown]
Trouble concentrating
Please rate your trouble concentrating in the last 7 days

[figure not shown]

Feeling tired (exhausted) during daytime
Please rate how tired you felt during daytime in the last 7 days

Feeling sleepy (drowsy) during daytime
Please rate how sleepy you felt during daytime in the last 7 days

ALLERGAN 3125-104-002 PART B

Likert Patient Depressive Symptom Scales (Clinic Evaluation)

[figure not shown]
Prior to Morning Dose

INSTRUCTIONS:

[figure not shown]
- Please complete all questions
- Read each question carefully
- Pay close attention to the specific time frame in each question
- For each question, circle the number from zero to ten, that best describes your symptoms and how you have been feeling, on average, during the time frame.

Difficulty falling asleep

[figure not shown]
Please rate your difficulty of falling asleep last night

Difficulty staying asleep

Please rate your difficulty of staying asleep last night

[figure not shown]

Problems waking up too early

Please rate your problems waking up too early last night

[figure not shown]

Overall Depression

[figure not shown]
Please rate your overall feelings of depression since your last dose of study medication

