4.2. Part B

The primary objective of Part B is to evaluate the efficacy of the change from baseline in MADRS total score at 7 days after the 1st dose of AGN-241751 (3 mg and 25 mg) compared with placebo in participants with MDD. The key secondary objectives are to evaluate the efficacy at Day 2, Day 11, Day 14, Day 18, and Day 21 after the 1st dose of AGN-241751 (3 mg and 25 mg) compared with placebo in participants with MDD. In addition, optional CSF samples will be collected in a subset of participants for PK analysis, and qEEG and ERP assessments will be collected in a subset of participants for pharmacodynamic analysis.

Objectives	Endpoints
Primary	

 To evaluate the efficacy at Day 7 of AGN-241751 compared with placebo in participants with MDD dosed BID 	
 Change from baseline in MADRS at 7 days after the first dose of treatment
Key Secondary	

 To evaluate the efficacy on Day 2, Day 11, Day 14, Day 18, and Day 21 (7 days after completion of dosing) after BID administration of AGN-241751 compared with placebo in participants with MDD dosed BID 	
 Change from baseline in MADRS total score at Day 2, Day 11, Day 14, Day 18, and Day 21

Objectives	Endpoints
Additional 
 Additional endpoints to be explored to determine differences between AGN-241751 and placebo in participants with MDD dosed BID Evaluation of pharmacodynamic endpoints (qEEG/ERP) and CSF between AGN-241751 and placebo in participants with MDD dosed BID 	
 Change from baseline in CGI-S total score by visit Rate of responders on MADRS at Day 2, Day 7, Day 11, Day 14, Day 18, and Day 21 Rate of remitters on MADRS at Day 2, Day 7, Day 11, Day 14, Day 18, and Day 21 Rate of responders on CGI-S by visit Time to first response on MADRS Time to first remission on MADRS Symptoms over time based on Likert Patient Depressive Symptom Scales Total recall scores at specified timepoints in HVLT-R Change from baseline in qEEG parameters collected during Day 1, Day 7, Day 14, and Day 21 Change from baseline in ERP parameters collected during Day 1, Day 7, Day 14, and Day 21 Descriptive analysis of CSF concentrations of AGN-241751

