- It is expected that participants in the double-blind treatment period will remain inpatient during the 1st week (Visit 2 to Visit 10/Discharge).
- During the inpatient treatment period, participants will have 7 visits (Visits 3 to 9); each visit will occur daily with no visit windows.
- At Visit 3 (Day 1) during the predose evaluation period, if there is a significant change (worsening or improvement in depressive symptoms) from the baseline Visit 2 (Day -1) MADRS based on the judgment of the PI, a MADRS assessment should be performed prior to the 1st dose of study medication.
- Participants will be discharged at Visit 10 (Day 8) after all predose assessments, morning dosing, and 4-hour postdose assessments are completed.
- During the inpatient treatment period, predose assessments will be performed prior to morning dosing at all inpatient visits (Visit 3 through Visit 10). Postdose assessments will be performed, as follows:
 - Visit 3 to Visit 6: 1, 2, 4, 8, and 12 hours after the morning dose (\pm 20 minutes)
 - Visit 7 to Visit 9: 4, 8, and 12 hours after the morning dose (\pm 20 minutes)
 - Visit 10: 4 hours after the morning dose (\pm 20 minutes)
- Within each timepoint, multiple assessments will be performed, as follows:
 - Assessments should be performed within \pm 20 minutes of each other
 - All psychiatric assessments (Likert Patient Depressive Symptom Scales, CSSR-S, MADRS, and CGI-S) are to be completed first prior to any other assessments (ie, qEEG, ERP) within the timepoint.
 - Participants are required to not use any nicotine substances 1 hour prior to administration of the HVLT-R.
- The afternoon dose of study medication is to be administered 8 hours (\pm 1 hour) after the morning dose.

[figure not shown]
Week 2 Outpatient Double-Blind Treatment Period

- During the outpatient treatment period, there will be 2 visits conducted every 3 days (Visit 11 [Day 11] and Visit 12 [Day 14/ET]). If necessary, these study visits may be conducted up to 1 day before or after the scheduled visit day.
- All participants who receive study medication should complete Visit 12 (Day 14/ET)
- At Visit 10 (Day 8) prior to discharge, the participant will be dispensed Bottle 2 of study medication (refer to Section 7.1.2 for dosing instruction). Participants will be instructed to bring the study medication bottle to Visit 11 for the site staff to confirm dosing compliance

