- The study medication bottle will be returned at Visit 12; site staff will confirm dosing compliance.

- A Patient Diary will be provided at Visit 10 and Visit 11 for completion by the participant at home. At Visits 11 and 12, the participant will return the diary, which was provided at the prior visit. Site staff will review the diary to confirm compliance and proper completion of the diary. At Visit 11 and Visit 12, prior to leaving the clinic, the participant will be given a new diary.
- The Patient Diary will include a Study Medication Dosing Log and Likert scales.
 - Study Medication Dosing Log: Participants will be instructed by site staff to record the date and time of the Visit 10 (Day 8) afternoon dose and each subsequent dose the participant has taken (morning and afternoon) at home, inclusive of doses on days when the participant has a clinic visit (Visit 11 [Day 11] and Visit 12/ET [Day 14/ET]).
 - Likert Patient Depressive Symptom Scales: Participants will be instructed by site staff to complete the Likert assessments at home on Day 9 and Day 10 (between Visit 10 and Visit 11) and on Day 12 and Day 13 (between Visit 11 and Visit 12/ET). The date and time each Likert assessment was completed are also to be recorded. The Likert assessments on days when the participant has a clinic visit (Visit 11 [Day 11] and Visit 12 [Day 14/ET]) will be completed by the participant in the clinic (ie, the participant will not complete the Likert assessment at home on these days).

Safety Follow-Up Period (Visit 13 [Day 18] and Visit 14 [Day 21])

- Participants completing the double-blind treatment period should enter the 1-week safety follow-up period. Participants who prematurely discontinue from the study before completing 2 weeks of double-blind treatment should complete the early termination (ET) visit and then enter the 1-week safety follow-up period.
 - A Patient Diary of Likert scales will be provided at Visit 12/ET (Day 14/ET) and at Visit 13 (Day 18). The Patient Diary will include Likert scales, and participants will be instructed by site staff to complete the Likert assessments at home on Days 15, 16, and 17 (between Visits 12 and 13) and on Days 19 and 20 (between Visits 13 and 14). The date and time each Likert assessment was completed are to be recorded. The Likert assessment on the day of Visit 13 will be completed by the participant in the clinic (ie, the participant will not complete the Likert assessment at home on this day).

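### Part B Likert: six items on the Day 1 predose form ask about the time since a dose not yet given, so the last pre-treatment rating cannot be answered as worded

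*Protocol*

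**What the plan says.** Section 4.2 of the protocol lists among the additional Part B endpoints "Symptoms over time based on Likert Patient Depressive Symptom Scales". Appendix 15 prints three forms, all scored 0 to 10:

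- **Screening.** The items look back over a week, for example "Please rate your overall feelings of depression in the last 7 days".
- **Prior to Morning Dose.** The three sleep items refer to the previous night, for example "Please rate your difficulty of falling asleep last night". The other six (depression, anxiety, irritability, concentration, daytime tiredness, daytime sleepiness) refer to dosing: "Please rate your overall feelings of depression since your last dose of study medication".
- **Post Dose.** The same six items plus one on interest or pleasure, all anchored on the last dose.

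Each form tells the participant to rate "how you have been feeling, on average, during the time frame".

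On timing, the schedule in Section 2.2 marks the Likert scales at Screening, Day -1 and Day 1 predose. Section 5.1.2 gives the first dose only once the Day 1 predose assessments are finished. Dosing runs through Day 14 (Section 7.1.2). Participants then "complete the Likert assessments at home on Days 15, 16, and 17" and on Days 19 and 20, with a clinic rating on Day 18. Section 9.1.5 places the Likert questions in a home diary but does not give the diary's recall wording. Section 10.3.2.2 makes the analysis exploratory and descriptive and leaves the detail to a Part B SAP; the SAP supplied covers Part A only.

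**The concern.** An endpoint that follows symptoms over time needs a pre-treatment starting point that measures the same thing as the later ratings. On the only form labelled for Day 1 predose, the six items that carry the mood, concentration and daytime content point to an event that has not happened. One participant may answer for the past week, another for the time since admission, and a third may leave the item blank. The data will not show which, so analysis cannot repair it.

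This is also the value that would become baseline if the general efficacy rule in Section 10.3.1 were applied, since that rule takes the most recent available score preceding the first dose. Section 10.3.1.3.2 names Day -1 for the parameters it lists, but the Likert scales are not in that list, and Section 10.3.2.2 names no baseline for them.

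The protocol fixes the look-back by visit for its other rating scales (Sections 9.1.2, 9.1.3, 9.4.6 and 9.4.7). Section 9.1.5 does not do so for the Likert scales, which suggests an oversight.

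The same anchor could matter again after Day 14. A recall period that starts at the last dose gets longer each day once dosing has stopped, so a return of symptoms would be averaged with earlier, better days.

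**Working it through.** The plan gives no figure of its own to reproduce, and Part B has no power calculation. The check is schedule arithmetic.

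**Step 1. Is there a reference dose at Day 1 predose?** The order on Day 1 is predose assessments, then first dose (Section 5.1.2). Doses taken before the rating = 0. Of the nine items on the morning form, 6 have no referent and 3 (sleep) are answerable.

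**Step 2. Which pre-treatment ratings of the six items exist, and how do they compare with later ones?** The afternoon dose is 8 hours (±1 hour) after the morning dose, so recall at the next morning's rating is 24 − 8 = 16 hours (24 − 9 = 15 to 24 − 7 = 17).

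| Rating | Form | Recall for the six items |
|---|---|---|
| Screening | Screening | 7 × 24 = 168 h |
| Day -1 | not stated | 168 h if the Screening form is reused; no referent if the morning form is used |
| Day 1 predose | Prior to Morning Dose | no referent |
| Days 2 to 8 predose | Prior to Morning Dose | about 16 h (15 to 17 h) |

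The one pre-treatment rating whose form is labelled and whose recall is defined covers 168/16 = 10.5 times the period of the morning ratings it would be compared with.

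**Step 3. What happens after Day 14, if the dose-anchored wording is kept?** This step is conditional, because the wording used in the diary and at the Day 18 visit is not shown. Recall in days = rating day − 14:

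| Day | 15 | 16 | 17 | 18 | 19 | 20 |
|---|---|---|---|---|---|---|
| Recall (days) | 1 | 2 | 3 | 4 | 5 | 6 |

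Assume the participant averages evenly over the period, as the form instructs. Let t be days since the last dose.

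- *Linear drift* at rate b from the last dose: mean over the period = bt/2, current level = bt, so the rating shows 50% of the current change on any day.
- *Step change* occurring s days after the last dose: share shown = (t − s)/t. On Day 20 (t = 6): s = 2 gives 4/6 = 67%; s = 3 gives 3/6 = 50%; s = 4 gives 2/6 = 33%. On Day 18 (t = 4): s = 2 gives 2/4 = 50%.

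For comparison, under a 24-hour recall on Day 20 the linear drift shows at (6 − 0.5)/6 = 92%, and each of these step changes shows at 100%.

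**The case against.** The case against acting has several parts, and much of it stands.

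- **A reader might infer that the Likert series has no valid baseline at all.** The documents do not support that. The sleep items work at Day 1 predose, the Screening form gives a defined 7-day score, and the form used at Day -1 is not stated. A 7-day form there would be plausible, because MADRS and CGI-S use a one-week look-back at Visits 1 and 2. What holds is narrower: for six items, no labelled pre-treatment rating both can be answered as worded and matches the later recall.
- **A reader might take the lengthening follow-up recall as established.** It is not. No diary or follow-up form is printed, so Step 3 applies only if the dose-anchored wording is carried over.
- **A reader might object that the 12-hour rating does not cover 12 hours.** That is not a defect. The 12 hours is an assessment time counted from the morning dose, not a recall length, and rating since the latest dose is a reasonable way to capture acute postdose effects.
- **The endpoint is not written as change from baseline, the analysis is descriptive, and all arms share the same forms.** This stands. The mismatch complicates each arm's trajectory but does not by itself create a difference between arms. MADRS on Days 18 and 21 remains the key secondary evidence on persistence.
- **The Part B SAP may settle the baseline.** It may, but a SAP cannot give meaning to a question that had none when it was answered.

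**Conclusion.** The point holds in a limited form. With the forms used as printed, six of the nine items on the Day 1 predose rating cannot be answered as worded. The only labelled rating of those items that is free of a dose reference has a recall about ten times as long as that of the later morning ratings. This rests on the printed forms and the order of events on Day 1, with no outside assumption.

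The dilution after Day 14 (50% of a linear drift; about 33% to 67% of a step change on Day 20, for changes 4 to 2 days after the last dose) rests on two assumptions: that the diary and clinic keep the dose-anchored wording, and that participants average evenly. If the diary uses other wording, those figures fall away and what remains is that the wording should be stated.

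The consequence is confined to an exploratory, descriptive endpoint. The primary and key secondary MADRS analyses are untouched. It is still worth correcting, because the remedy is a change of wording and the loss cannot be recovered afterwards.

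**What to change.** 1. In Appendix 15 and the diary, give the six items a fixed recall that does not refer to dosing, for example the last 24 hours, at Day -1, at Day 1 predose, at the daily morning ratings these are compared with, and at the outpatient and follow-up ratings at home and in clinic.
2. State in Section 9.1.5 or the Section 2.2 schedule which form applies at each of those timepoints.
3. Name the Day 1 predose rating as the Likert baseline in the Part B SAP.

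The sleep items on the morning form need no change, and the inpatient Post Dose form can keep its dose-anchored wording.

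The cost is reworded forms and diary plus one line in the SAP, with no added assessments. The downside is that participants already rated on the old wording are not directly comparable with later ones on these items. They need a flag, so that the descriptive summaries can be shown with and without them.

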**Overall Anxiety**

Please rate your overall feelings of anxiety since your last dose of study medication

[figure not shown]
**Overall Irritability**

Please rate your overall feelings of irritability since your last dose of study medication

[figure not shown]

Trouble concentrating

[figure not shown]
Please rate your trouble concentrating since your last dose of study medication

[figure not shown]
**Feeling tired (exhausted) during daytime**

Please rate how tired you felt during daytime since your last dose of study medication

**Feeling sleepy (drowsy) during daytime**

Please rate how sleepy you felt during daytime since your last dose of study medication

ALLERGAN 3125-104-002 PART B

Likert Patient Depressive Symptom Scales

[figure not shown]
Post Dose Assessments

INSTRUCTIONS:

[figure not shown]
- Please complete all questions
- Read each question carefully
- Pay close attention to the specific time frame in each question
- For each question, circle the number from zero to ten, that best describes your symptoms and how you have been feeling, on average, during the time frame.

Overall Depression

[figure not shown]
Please rate your overall feelings of depression since your last dose of study medication

**Overall Anxiety**

Please rate your overall feelings of anxiety since your last dose of study medication

[figure not shown]
**Overall Irritability**

Please rate your overall feelings of irritability since your last dose of study medication

[figure not shown]

Trouble concentrating

[figure not shown]
Please rate your trouble concentrating since your last dose of study medication

**Feeling tired (exhausted) during daytime**

Please rate how tired you felt during daytime since your last dose of study medication

**Feeling sleepy (drowsy) during daytime**

Please rate how sleepy you felt during daytime since your last dose of study medication

Interest or pleasure doing things
Please rate your interest or pleasure doing things you usually enjoy
since your last dose of study medication

12.16. Appendix 16: Hopkins Verbal Learning Test-Revised (Part B Only)

Due to copyright restriction, the HVLT-R scale is not included.

12.17. Appendix 17: Karolinska Sleepiness Scale (Part B Only)

Karolinska Sleepiness Scale (KSS)

Instructions: Here are some descriptors about how alert or how sleepy you might be feeling right now. Please read them carefully and CIRCLE the number that best corresponds to the statement describing how you feel at the moment.

(Please try to respond according to how you have been feeling in the last 5 minutes)

CIRCLE THE BEST ANSWER:

- 1 Extremely alert
- 2 Very alert
- 3 Alert
- 4 Rather alert
- 5 Neither alert nor sleepy
- 6 Some signs of sleepiness
- 7 Sleepy, but no difficulty remaining awake
- 8 Sleepy, some effort to keep alert
- 9 Extremely sleepy, fighting sleep

References:

12.18. Appendix 18: CSF Sample Collection, Handling, and Storage Instructions (Part B Only)

A local anesthetic may be applied to minimize discomfort to the subject. Once the spinal needle is inserted to the lumber region (eg, L3-4 or L4-L5), collect approximately 4 mL of CSF fluid at a rate of 0.5 mL/minute. This collection is carried out under ambient conditions. Upon completion, transfer harvested CSF immediately into 4 prechilled, labeled polypropylene cryovials (Nalgene® 1.5 mL polypropylene External Thread Cryogenic Vials, Catalog #5000-1020), placing approximately 1 mL in each of the 4 polypropylene vials. Tubes should be labeled with the study number, participant identification number, date, and timepoint. Immediately place and store upright the frozen tubes in freezer maintained at nominal -20°C ±10°C. Samples will be batched and shipped according to the sponsor or at the end of the study.

12.19. Appendix 19: Sample Shipment Guide (Part B Only)**BIOLOGICAL SAMPLES INCOMING TO KEYSTONE BIOANALYTICAL**

Samples will be batched and shipped according to the sponsor or at the end of the study.

Ship CSF samples on sufficient dry ice to keep them frozen for a minimum of 96 hours.

Sample Packing

- Place the samples by subject number in compartmentalized boxes, label the box(es) with study number and subject number(s). Place the box in a freezer bag(s)
- Place the samples in a thick-wall foam shipping box (eg, 19" x 19" x 12") that has a slab of dry ice on the bottom and on 2 of the 4 sides. Pack the remaining spaces with dry ice or ice pellets
- Make a note in the source documents, air bill, and shipping box of the estimated weight of the dry ice used per box
- Put lid on box and seal lid with tape
- To the lid of the box, attach a sample transfer record and an inventory of the samples contained inside (eg, 3125-104-002 CSF samples, Subject 301-001-001, Subject 301-001-002). Include a note explicitly stating any scheduled samples that may have been missed or not included in the shipment
- Put the box in a cardboard shipping carton, if available, and seal

Shipping Label

- Mark the outside of the cartons with the tally number (1 of 5, 2 of 5, etc.)
- Affix to each box an address label with the following information:

[name]

Keystone Bioanalytical, Inc.

[name]

[name]

- Put 1 "PERISHABLE GOODS" label on each carton
- Mark each carton "KEEP FROZEN"

